4. PARTICIPANT ENTRY

PRE-RANDOMISATION EVALUATIONS

Potential participants will be interviewed and examined by one of the research doctors. They will be asked to complete a medical and lifestyle questionnaire and have blood tests and height, waist and weight measurements to calculate body mass index. They will have an electrocardiogram (ECG) and fasting blood samples will be taken. They will be asked to undergo a glucose tolerance test. All women of child bearing age will have a pregnancy test.

INCLUSION CRITERIA

Study 1: Healthy men and women aged between 18 and 70 years with BMI between 20-25 kg/m² and with normal fasting blood glucose (below 5.5 mmol/l and HbA1C less than 5.7%) will be eligible to volunteer.

Study 2: As for Study 1.

Study 3:

Cohort 1: Volunteers aged between 30 to 70 with a BMI between 25-35 kg/m² who do not have impaired fasting glucose and have HbA1c below 5.7%.

Cohort 2: Volunteers aged between 30 to 70 years with a BMI between 25-35 kg/m² who have impaired fasting glucose (between 5.5-7 mmol/l) and HbA1C between 5.7% and 6.5%,

EXCLUSION CRITERIA

- Type 1 or Type 2 Diabetes
- Gained or lost ≥ 3 kg weight in the past three months
- Taken prescription medicines having an impact on metabolism, appetite regulation, glucose homeostasis and hormonal regulation
- Taken any dietary supplements in the last 6 months
- Any chronic illness
- Cardiovascular disease
- Excess alcohol intake
- Current smokers
- Any gastrointestinal disorder e.g. Crohn's disease, coeliac disease or irritable bowel syndrome
- A history of drug or alcohol abuse in the last 2 years
- Pregnancy (all women of child bearing age will undergo a pregnancy test).
- Pancreatitis
- Use of medications likely to interfere with glucose metabolism, appetite regulation, hormonal balance.

Any participants with the above conditions would have an altered pattern of glucose homeostasis and would therefore give confounding or misleading results.

WITHDRAWAL CRITERIA

The safety of the study participants takes priority. Any significant adverse event (as assessed by the researchers) will halt the study and the ethics committee and sponsor will be informed as per standard protocol. All adverse events will be recorded and investigators will review each adverse event as it arises. In addition, participants will be free to withdraw at any time and are not required to give a reason.

5. ADVERSE EVENTS

Adverse Event (AE): Any untoward medical occurrence in a patient or clinical study subject.

Serious Adverse Event (SAE): Any untoward and unexpected medical occurrence that:

- results in death
- is life- threatening – refers to an event in which the subject was at risk of death at the time of the event; it does not refer to an event which hypothetically might have caused death if it was more severe.
- requires hospitalisation, or prolongation of existing inpatients' hospitalisation.
- results in persistent or significant disability or incapacity
- is a congenital abnormality or birth defect

Medical judgement should be exercised in deciding whether an AE is serious in other situations. Important AEs that are not immediately life threatening or do not result in death or hospitalisation but may jeopardise the subject or may require intervention to prevent one of the other outcomes listed in the definition above, should also be considered serious.

REPORTING PROCEDURES

All adverse events should be reported to the Sponsor, the local ethical review committee and the local research and development office. Depending on the nature of the event the reporting procedures below should be followed. Any questions concerning adverse event reporting should be directed to the Chief Investigator in the first instance.

Non serious AEs

All such events, whether expected or not, will be recorded.

Serious AEs

An SAE form should be completed and faxed to the Chief Investigator within 24 hours. However, relapse, death and hospitalisations for elective treatment of a pre-existing condition do not need reporting as SAEs.

All SAEs should be reported to the London – West London Research Ethics Committee where in the opinion of the Chief Investigator the event was:

- ‘related’, i.e. resulted from the administration of any of the research procedures; and
- ‘unexpected’, i.e. an event that is not listed in the protocol as an expected occurrence.

Reports of related and unexpected SAEs should be submitted within 15 days of the Chief Investigator becoming aware of the event, using the NRES SAE form for non-IMP studies.

Local investigators should report any SAEs as required by their Local Research Ethics Committee and/ or Research and Development Office and to the Sponsor.

AMMENDMENTS

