Visit 2 and 3: Participants will undergo a frequently sampled intravenous glucose tolerance test (IVGTT) to detect changes in insulin sensitivity and beta cell function. The day prior to the study subjects will be asked to refrain from alcohol and strenuous exercise and fast for 12 hours prior to the study. The study will be carried out at the St. John Mc Michael Centre (Hammersmith hospital). Subjects will have two cannulae placed in separate peripheral veins. Subjects will be given glucose (20% solution-0.3g/kg) directly into a peripheral vein following oral administration of propionate at the most effective dose determined in study 2. Timing of the glucose bolus will be determined from data gathered in study 1 and be given 5mins prior to the expected plasma peak concentrations of sodium propionate. Blood samples (10ml) will be taken at, -5, 0, 2, 4, 6, 8, 10, 19, 22, 30, 40, 50, 70, 100 & 180 where glucose is administered at time 0, in total 150ml of blood will be drawn. Participants will be administered human insulin (0.03units/kg, 'regular human insulin – Novo Nordisk') at 20 mins post glucose. Participants will be asked to attend a repeat visit with a minimum of a week between visits. Participants will be randomly assigned propionate or placebo.

Blood samples will be analysed using the following methods:

- Propionate by Mass spectrometry

- Insulin, GLP-1, PYY, leptin and non-esterified fatty acids will be measured using commercially available kits.
- Glucose will be measured using a glucometer.
-

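### The SAE definition builds in expectedness, so on a literal reading a serious event regarded as foreseeable can miss SAE classification and the 24-hour form

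*Combined protocol and SAP*

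**What the plan says.** All of the reporting rules at issue are in Section 5 (Adverse Events).

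- **Adverse event:** "Any untoward medical occurrence in a patient or clinical study subject". Expectedness plays no part.
- **Serious adverse event:** "Any untoward and unexpected medical occurrence that" meets at least one listed criterion, for example that it "requires hospitalisation, or prolongation of existing" inpatient care.
- **Non-serious events:** "All such events, whether expected or not, will be recorded".
- **Serious events, first step:** "An SAE form should be completed and faxed to the Chief Investigator within 24 hours". A closing line also has local investigators report SAEs to the sponsor and to local bodies.
- **Serious events, ethics committee:** only SAEs that the Chief Investigator considers both related and unexpected are sent. Here, and only here, *unexpected* is explained: "an event that is not listed in the protocol as an expected occurrence". On timing: "Reports of related and unexpected SAEs should be submitted within 15 days of the Chief Investigator becoming aware of the event".
- **All adverse events:** a general sentence under Reporting Procedures sends every adverse event to the sponsor, the ethics committee and the research and development office. It sets no deadline.

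Two other places bear on the point. Section 4 (Withdrawal Criteria) has all adverse events recorded, and says that a significant one halts the study, with the ethics committee and sponsor informed. Section 3 (Study 3, Visits 2 and 3) describes procedures after which a serious event could be thought foreseeable: an intravenous glucose bolus, and then "Participants will be administered human insulin (0.03units/kg", with the insulin given 20 minutes after the glucose.

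**The concern.** Seriousness describes the outcome of an event. Expectedness describes whether it was anticipated. Reporting systems normally keep the two apart: seriousness decides how fast an event is escalated, and expectedness decides which of the serious events go further. Section 5 makes expectedness part of seriousness and then applies it a second time.

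The serious events most likely to be called foreseeable are those that follow study procedures. If that view is enough to take an event out of the SAE definition, it also takes the event out of the one step with a short deadline, the 24-hour form. If different staff read the word differently, identical events will be classified differently, and an SAE tabulation would then depend partly on who made the classification.

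**Working it through.** No formula applies and the plan gives no figure to reproduce. The check is to read the provisions of Section 5 against one another.

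1. **Definition against definition.** The AE and SAE definitions open alike, except that the SAE definition adds *and unexpected*. Read literally, an event must pass two tests to be an SAE: it meets a seriousness criterion, and it is unexpected.

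2. **Definition against committee rule.** The committee rule selects SAEs that are related and unexpected. If the word means the same in both places, every SAE has already passed the second condition, so that condition removes nothing. It does work only if some SAEs are expected, and the definition rules that out.

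3. **What the word means in the definition.** Take a hospitalisation after a Study 3 procedure that staff regard as foreseeable and that is not on any list of expected occurrences.
   - *Staff judgement:* the event is expected, fails the SAE definition, and the 24-hour form is not triggered.
   - *Not listed in the protocol:* the event is unexpected, is an SAE, and the 24-hour form is due.

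   The explanation of the word is attached to the committee rule only. The definition does not refer to it.

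4. **Whether another clause catches the event on the first reading.**
   - The non-serious rule covers expected events, but its heading does not fit a hospitalisation, and no matching words cover serious events.
   - The other-situations clause starts from AEs, with no expectedness condition, so it recovers some events. It is aimed mainly at events short of death or hospitalisation. Its conditions are joined by *or*, so a hospitalised event that is not immediately life threatening might be argued into it, but not clearly.
   - The general AE sentence does apply. The event is reported as an AE, without an SAE form and without a deadline.

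5. **Which reports are affected.** If the word has one meaning throughout, the 15-day committee report is the same with or without the two extra words, because its own filter removes expected events. The effect falls on the 24-hour form and on SAE reports to the sponsor and local bodies.

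6. **Exposure, for scale only.** Study 3 plans 34 + 34 = 68 participants with two IVGTT visits each, so 68 × 2 = 136 insulin administrations. This counts occasions on which the question could arise. It is not a count of events, still less of misclassified ones.

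**The case against.** The strongest reply is that the protocol explains *unexpected* once, as not listed, and that this meaning should carry over to the definition. Any unlisted serious event is then an SAE, the definition excludes it from nothing, and the fault is a redundant phrase. This reading is reasonable, and it defeats any flat statement that a hospitalisation after the Study 3 insulin is not an SAE. It does not remove the point, because the definition does not adopt that meaning and a careful reader could apply the ordinary one.

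A second reply is that such an event is not lost, and this stands in full. A reader might infer that it would merely be recorded. Section 5 requires every AE to be reported to the sponsor, the ethics committee and the research and development office, and Section 4 adds the halt and notification for a significant event. What can be lost is the SAE label, the 24-hour form and the SAE-specific reports.

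A third reply is that the two rules can both be obeyed, so they do not strictly conflict. That is also fair: on a single meaning the second filter is redundant rather than impossible to apply. But a redundant filter suggests that the definition was not meant to contain the word.

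**Conclusion.** The point holds as a wording defect in safety reporting with a practical consequence. On a literal reading, a serious event regarded as foreseeable could miss SAE classification, the 24-hour form and SAE-specific sponsor and local reporting, while still being recorded and reported as an AE with no stated deadline. The conclusion assumes that *unexpected* in the definition may be read as staff judgement, which the text neither states nor excludes. It should be corrected, and the general AE reporting limits the harm.

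Two stronger readings are not supported. A reader might infer that the trial's SAE count will be biased downwards. The documents give no event rate, and Section 7 (Statistics and Data Analysis) plans no safety analysis, so undercounting is a possibility of unknown size. A reader might also infer that the protocol lists no expected events at all. No list appears in the text available, but some pages were removed from it, so absence from the full protocol cannot be asserted. The verdict does not depend on it.

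**What to change.** Delete *and unexpected* from the SAE definition in Section 5, so that seriousness alone triggers the 24-hour form and SAE reporting to the sponsor and local bodies. Keep expectedness only in the 15-day ethics-committee rule, where it is already explained.

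The cost is two words in the protocol and possibly a few more SAE forms. No visit, sample size or analysis changes.

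What belongs on a list of expected occurrences is for the investigators and sponsor to decide and is not part of this fix. Any event placed on such a list drops out of the 15-day report, so adding procedure-related events to it would reduce what the committee sees.

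### Section 5 makes death the first criterion for an SAE, then exempts death from reporting as an SAE, so the 24-hour form can be skipped for an unexpected death

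*Combined protocol and SAP*

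**What the plan says.** All of the conflicting text is in section 5 of the protocol.

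- **Definition.** An SAE is an untoward and unexpected occurrence that meets one of a list of criteria. The first is that it "results in death". Others cover a life-threatening event, which "refers to an event in which the subject was at risk of death at the time of the event", and one that "requires hospitalisation, or prolongation of existing" inpatient stay.
- **Form.** Under Serious AEs: "An SAE form should be completed and faxed to the Chief Investigator within 24 hours".
- **Exemption.** The next sentence, introduced by However, says that "relapse, death and hospitalisations for elective treatment of a pre-existing condition do not need reporting as SAEs".
- **Ethics report.** A separate paragraph then sends all SAEs to the ethics committee where the Chief Investigator judges them both related and unexpected. The limit is 15 days from the Chief Investigator becoming aware.
- **Local report.** Local investigators report SAEs to the Sponsor and as their local bodies require. No time limit is given.
- **General rule.** "All adverse events should be reported to the Sponsor, the local ethical review committee and the local research and development office". No time limit is given here either.

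Section 4, Withdrawal Criteria, adds that investigators review each adverse event when it occurs. It also says that a significant event halts the study, with the ethics committee and sponsor informed under a standard procedure that the text does not describe.

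**The concern.** The definition and the exemption cannot both govern a death. By the first, an unexpected death is an SAE; by the second, it need not be reported as one. Staff who follow the exemption as written may leave out the SAE form, and its 24-hour limit, for the gravest outcome on the list.

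The effect may go further. The exemption speaks of reporting as SAEs in general, and the ethics paragraph that follows does not say whether an exempted event is still covered. The 15-day period also starts only when the Chief Investigator becomes aware, and the form is the only route to the Chief Investigator with a stated time limit. A skipped form could therefore delay the ethics report even if that report is still required.

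What is at stake is the timeliness of safety reporting, not the estimation of any treatment effect.

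**Working it through.** No sample size, power or error rate is involved. The check is a comparison of the rules, followed by a count of stated deadlines.

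**Step 1: does the exemption have a limiting condition?** The phrase about elective treatment of a pre-existing condition fits hospitalisations and cannot sensibly qualify death. If the pre-existing condition is nevertheless stretched to cover death, some deaths are still exempt although death defines an SAE, so the conflict remains. Hospitalisation shows the contrast. It too is an SAE criterion, but its exemption is confined to elective admissions, so criterion and exemption can coexist. For death they cannot.

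**Step 2: what deadlines exist?** The Serious AEs text has three routes: the form (24 hours), the ethics report (15 days, if related and unexpected) and the local and Sponsor report (no stated limit). That is 3 routes and 2 stated deadlines.

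**Step 3: how many deadlines are lost?** The count depends on the type of death, because the SAE definition itself requires the event to be unexpected.

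- *Unexpected and related.* Both deadlines would apply.
  - Filed under the life-threatening or hospitalisation criterion: both are kept, 2 − 2 = 0 lost.
  - Exemption covers the form only: one is kept, 2 − 1 = 1 lost.
  - Exemption covers all SAE reporting: none is kept, 2 − 0 = 2 lost.
- *Unexpected and unrelated.* The ethics report never applied, so only the 24-hour limit is in play: 0 or 1 lost.
- *Expected.* The event falls outside the SAE definition, so neither deadline applied: 0 lost.

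**Step 4: does anything else close the gap?** A death is still covered by three other provisions: the general adverse event rule in section 5, and the halt-and-notify rule and the review of each event in section 4. None states a time limit, and none restores the SAE route. Section 5 also says: "Any questions concerning adverse event reporting should be directed to the Chief Investigator in the first instance". That gives staff someone to ask, but it does not settle the text.

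**The case against.** The strongest reply is that little is lost in practice. The exemption is permissive: staff who file a form for a death breach nothing. The form goes only to the Chief Investigator, while the Sponsor, ethics committee and research office are covered by the general rule. Each event is reviewed when it occurs, and a significant one halts the study. A fatal event will often meet another SAE criterion as well. All of this stands, and it limits the point to a lost deadline and an unclear one.

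Four stronger readings are tempting, and the documents do not support them.

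- *Deaths would go unreported.* They would not; the general rule and section 4 still apply.
- *The 15-day ethics report is lost.* That is only possible. The ethics paragraph is separate and opens by referring to all SAEs.
- *The section issues two opposite commands.* It sets a definition against a permissive exception. That is a real conflict, but not two opposed orders.
- *The seriousness paragraph is a second contradiction.* It concerns "Important AEs that are not immediately life threatening or do not result in death or hospitalisation but may jeopardise the subject", and so by its terms not fatal events. It shows how odd the exemption is, since a lesser event is treated as serious with no exemption, but it is a contrast only.

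It could also be said that deaths from underlying disease were meant. Section 4 excludes any chronic illness, which makes that intention unlikely. It does not rule it out, since Study 3 admits people up to age 70 with BMI up to 35 and impaired fasting glucose. Either way, the sentence does not state such a limit.

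**Conclusion.** The point holds as an internal inconsistency in safety reporting that is wrong as written. For an unexpected death, the literal text removes the 24-hour form. If the death is also related, the status of the 15-day report is ambiguous. The range is 0 to 2 stated deadlines lost for an unexpected, related death, 0 to 1 for an unexpected, unrelated one, and 0 for an expected one.

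This rests on two assumptions: that the word unexpected in the SAE definition is applied as written, and that no text outside the parts available for review clarifies the rule. A clarification elsewhere would help staff but would not remove the conflict within section 5.

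A reader might infer that exempting deaths was a deliberate design choice, or that the trial's results are at risk. Nothing in the text shows the first, and no efficacy result is affected. The case for correction rests on a wrong safety instruction that is easily put right, not on how likely a death is.

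**What to change.** Delete death from the exempting sentence in section 5, so that it covers only hospitalisations for elective treatment of a pre-existing condition. Delete relapse at the same time: it does not bear on the contradiction, but it has no evident meaning in healthy or at-risk volunteers. Then check the revised sentence against the SAE definition in the same section, so that every event meeting the definition follows the form and ethics routes unless it is an elective hospitalisation of that kind.

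The cost is a few deleted words and one cross-check, with no added visit, sample or procedure. Section 8 describes the study as awaiting ethical approval; if approval has since been given, the change needs an amendment.

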7. STATISTICS AND DATA ANALYSIS

An independent researcher (i.e. not linked to the study) will be given the task of randomisation, which will be by sealed envelopes.

Although the data handling and statistical methodology can only be confirmed once all the data is collected. Our intention is to use parametric techniques to analyse the data if it is normally distributed. We will therefore use T-tests for comparisons between two groups and ANOVA for comparisons of three or more groups.

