undergo a pregnancy test and will be informed that they should not plan to become pregnant whilst participating in the study.

TREATMENT	Participants in the Intervention groups will receive enteric coated capsules containing sodium propionate. Participants in the Control group will receive sodium chloride in the same capsule formulation. For each study one dose per visit will be taken.
DURATION	
Study 1: Individuals participating in the dose ranging study will be asked to attend our clinical trials unit on a single day for a total of 8 hours. Volunteers taking part in the full pharmacokinetic study will be asked to attend the clinical trials unit twice for a total of 8h at each visit.
 
Study 2: Individuals will be asked to attend the clinical trials unit on 5 separate occasions each visit lasting 4 hours during which oral glucose tolerance testing will take place.
 
Study 3: All participants will be asked to attend the clinical trials unit to undertake an oral glucose tolerance test in order to screen for impaired glucose tolerance. Individuals will be asked to attend the clinical trials unit on two separate occasions each visit lasting 4 hours for the main part of the study.

MEASURES	
Study 1: The primary outcome will be peak plasma concentration of propionate coupled with determination of the elimination profile. Secondary outcomes will aim to understand the acute effects of propionate and will include plasma insulin, glucagon like peptide-1 (GLP-1), peptide yy (PYY), leptin, glucose and free fatty acid concentrations following propionate administration.
 
Study 2: Our primary outcome will be the insulinogenic index which is the increase in plasma insulin from 0-30mins during an oral glucose tolerance test. Secondary outcomes will be plasma concentrations of insulin, Glp-1, free fatty acids, PYY, leptin, glucose and free fatty acids will be measured during the oral glucose tolerance test.
 
Study 3: The primary outcome will be measurement of beta cell function as determined by the calculation of acute insulin response to glucose (the incremental area under the insulin profile from 0-10minutes following an intravenous glucose bolus) during an intravenous tolerance test.
 
Secondary outcomes will be plasma concentrations of insulin, GLP-1, PYY, Leptin glucose and free fatty acids.

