Study Day1: Using the data from the dose ranging study a full pharmacokinetic study will be undertaken. Participants will arrive at the St. John McMichael Centre (Hammersmith

hospital) having fasted from the previous evening and a canulae will be inserted into a peripheral vein. Blood samples (10ml) will be taken at -10 and 0 post oral propionate administration (3g) then 4 samples will be taken during each of the absorption and early elimination phases, followed by further samples post peak for a total of 6 samples in this phase, over three half-lives. In total 120mls of blood will be drawn.

Study Day 2: At least a week following the first study day participants will be asked to attend a repeat visit at the St John Mc Michael Centre which will follow the same protocol as for study day 1 but participants will be given a 6g dose of propionate.

Blood samples will be analysed using the following methods:

- Propionate by Mass spectrometry
- Insulin, GLP-1, PYY, leptin and non-esterified fatty acids will be measured using commercially available kits.
- Glucose will be measured using a glucometer.

Study 2

Aim: To dose dependently determine if propionate augments beta cell function.

Study methodology: Participants will undergo a series of oral glucose tolerance tests (OGTT) following administration of propionate. Each participant will receive all doses of propionate and each study day will be separated by at least 1 week.

Participants: 30 healthy men and women aged 18-70, body mass index (BMI) 20-25 kg/m², with normal fasting glucose and HbA1C.

Support for number of participants: A previous small study of the effects of propionate on glucose levels in humans identified a 47.4% reduction in glucose AUC over 2 hours following consumption of a standard 50 g carbohydrate load supplemented with propionate. Mean OGTT glucose AUC in a group of 514 healthy subjects was 40.8 mmol.min (SD 7.1 – unpublished data from the study described in Diabetic Medicine 2007;24:1269-1278). A 47.4% reduction in OGTT glucose AUC would result in a mean glucose AUC of 21.5. Using data from the same study, a mean insulinogenic index of 0.99 (SD 0.85) was observed, regression analysis estimated that a 47.4% reduction in glucose AUC would be associated with an increase in insulinogenic index of 0.73 SD. This can be detected as significant at p<0.05, with 80% power using 30 in each group. Screen failures will be replaced.

Health Screening and enrolment Visit

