Study methodology: Participants will undergo intravenous glucose tolerance tests. The effect of propionate on beta cell function will be determined in a randomised double blind placebo controlled crossover study.

Participants:

Cohort 1: 34 healthy men and women aged 30-70, body mass index (BMI) 25-35 kg/m², normal fasting blood glucose (below 5.5mmol/l and HbA1C less than 5.7% will be eligible to volunteer. Screen failures will be replaced.

Cohort 2: 34 men and women at risk of developing diabetes aged 30-70 with a body mass index (BMI) 25-35 kg/m² with fasting blood glucose between 5.6mmol/l and HbA1C between 5.8 and 6.5% will be eligible to volunteer. Screen failures will be replaced.

Support for number of participants: Our pilot data demonstrates mean Insulin AUC₁₀ of 8.1 for saline treated mice versus 11.3 for mice propionate-treated mice, an increase in the acute insulin response to glucose of 40%. Mean IVGTT-AIRg in a group of 306 healthy subjects was 492 mU.min (SD 48.7 - unpublished data from the study described in Diabetologia 2004;47:1157-1166). Using log-transformed data for IVGTT-AIRg, it was estimated that a 40% increase in IVGTT-AIRg would constitute an increase of 0.79 SD, which could be detected as significant at p<0.05, with 90% power using 34 in each group. Screen failures will be replaced.

Health Screening and enrolment Visit

Participants will arrive fasted from 8pm the previous evening. They will be clerked and examined by a research doctor. Measurements of height, weight, body fat content, blood pressure, an ECG and a blood test (for full blood count, urea and electrolytes, liver function tests, lipid profile, fasting glucose, HbA1C) will be taken. Screen failures will be replaced.

Visit 1: Oral glucose tolerance test.

The participant will be asked to come to the Clinical Investigations Unit at Hammersmith Hospital at 8:30am, having fasted from 8pm the previous day. A cannula will be inserted into a peripheral vein and two fasting blood samples taken at -30 and -10 mins before the participant consumes a drink containing 75 g of glucose. During the next 3 hours blood samples will be taken at 0, 10, 20, 30, 60, 90, 120, 180 minutes post glucose administration. A total of 100ml of blood will be taken.

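### Section 7 leaves the primary analysis method to be chosen after the data are in, on an undefined normality check, and does not carry over the log scale on which Study 3 was sized

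*Combined protocol and SAP*

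**What the plan says.** Section 7 (Statistics and Data Analysis) is the whole analysis plan apart from one sentence on randomisation. It states that "the data handling and statistical methodology can only be confirmed once all the data is collected", and then: "Our intention is to use parametric techniques to analyse the data if it is normally distributed". The tests named are these: "We will therefore use T-tests for comparisons between two groups and ANOVA for comparisons of three or more groups". Nothing is said about how normality will be judged, or whether raw values, within-person differences or residuals will be examined. Nor does it say what follows if the check fails, or whether the tests will be paired.

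Elsewhere the protocol already holds information about scale and design:

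- **Study 2.** The Study Summary defines the primary outcome: "Our primary outcome will be the insulinogenic index which is the increase in plasma insulin from 0-30mins during an oral glucose tolerance test". Section 3 reports that "a mean insulinogenic index of 0.99 (SD 0.85) was observed". Every participant receives all five dose levels, and the Study Summary describes the study as open label.
- **Study 3.** This is a randomised, double-blind, two-period crossover. Its sample-size paragraph prints AIRg as 492 with SD 48.7, and then says: "Using log-transformed data for IVGTT-AIRg, it was estimated that a 40% increase in IVGTT-AIRg would constitute an increase of 0.79 SD".

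**The concern.** Two things are at stake.

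The first is the status of the primary p-values. If the method is settled only when the data are complete, and the branch depends on an unspecified check, several defensible analyses remain open when the results are known. Choosing among them, even in good faith, means that the nominal 5% no longer describes the procedure. Blinding gives no protection in Study 2 if it runs open label.

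The second is consistency between sizing and analysis. Study 3's 0.79 SD and 90% power are log-scale statements. If AIRg is analysed untransformed, the power claim refers to a different analysis. Study 2's mean and SD also give early warning that a normality check on the raw index may well fail, and the plan has no branch for that case.

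**Working it through.** **1. The plan's own sample sizes.** For two independent groups, two-sided α = 0.05 (sidedness assumed) and n per group, power ≈ Φ(d·√(n/2) − 1.96).

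- Study 2: d = 0.73, n = 30. Φ(0.73 × 3.873 − 1.96) = Φ(0.87) = 80.7%. The t-based value is 79.4%. The stated 80% is reproduced.
- Study 3: d = 0.79, n = 34. Φ(0.79 × 4.123 − 1.96) = Φ(1.30) = 90.3%. The t-based value is 89.4%. The stated 90% is reproduced.

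Both figures come from an independent-groups calculation, although both studies are within-person. Section 7 does not settle which structure the analysis will use.

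**2. Study 3 scale.**

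- Log SD implied by the log-scale sentence: ln(1.4)/0.79 = 0.3365/0.79 = 0.426. That is a coefficient of variation of √(exp(0.426²) − 1) = 0.446, or a raw SD of about 0.446 × 492 = 219.
- Printed SD: 48.7/492 = 0.099. A 40% rise is 0.40 × 492 = 196.8, and 196.8/48.7 = 4.04 SD. On the log scale it is 0.3365/0.0987 = 3.4 SD.

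The printed SD and the 0.79 SD cannot describe the same variable on corresponding scales. The printed figures on their own look close to symmetric (lognormal skewness about 0.3). Only the log-transform sentence points to skew.

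**3. Study 2 shape.** Mean − 2 SD = 0.99 − 1.70 = −0.71. A normal variable would have Φ(−0.99/0.85) = 12% of values below zero. This suggests right skew but does not identify the distribution.

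**4. Does the scale matter for Study 2 power?** Simulated paired t-tests between two visits, n = 30, with mean 0.99 and SD 0.85 matched. Assumed, because the documents do not give them: distribution shape, a multiplicative effect, and correlation 0.5.

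| Shape | Rise | Raw scale | Log scale |
|---|---|---|---|
| Lognormal (log SD = √ln(1 + (0.85/0.99)²) = 0.743) | 1.4-fold | 52% | 67% |
| Gamma | 1.4-fold | 49% | 41% |
| Lognormal | 1.63-fold | 82% | 94% |
| Gamma | 1.63-fold | 81% | 71% |

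The 1.63-fold rows read Study 2's 0.73 SD as a shift in the raw mean: (0.99 + 0.73 × 0.85)/0.99 = 1.63. The 1.4-fold rows are illustrative. The direction of the difference reverses with the assumed shape.

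**5. Cost of choosing afterwards.** Under the null, with lognormal data, 30 pairs and correlation 0.5, each of the raw paired t, log paired t and Wilcoxon tests taken alone runs at about 5%. Reporting whichever gives the smallest p-value rejects in about 8% of trials (separate simulations gave 7.5% to 8%). The same exercise for Study 3 gives about 7%.

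**The case against.** The strongest reply is that Section 7 commits to nothing wrong. T-tests and ANOVA are offered only if the data are normal, so a skewed outcome is not sent to a raw-scale test. The team also used the log scale for AIRg when sizing Study 3 and would presumably do so again.

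The first part stands. A reader might infer that the plan prescribes a raw-scale analysis of skewed data and so throws away a definite amount of Study 2 power, perhaps 10 to 15 points. The documents do not support that. The tests are conditional, the loss needs an assumed lognormal shape, and a gamma with the same mean and SD makes the log scale the weaker choice. Even under the lognormal, the raw test at Study 2's own effect size reaches 82%, above the planned 80%.

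A reader might also infer that the protocol's figures show both outcomes to be skewed. They do not for AIRg, where the printed mean and SD look nearly symmetric. At the planned 40% effect the log scale gains Study 3 little in any case: with log SD 0.426 and two independent groups of 34, power is 86.9% raw against 89.7% log.

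What does not stand is the suggestion that the normality condition settles the method. It does not say what is tested. In a lognormal illustration with n = 30 and correlation 0.5, a Shapiro-Wilk test rejects raw values in about 94% of samples but within-person differences in only about 60%, so the branch taken depends on an unstated choice. When the check fails, there is no branch at all. That the log scale was used for sizing is not a statement that it will be used for analysis.

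**Conclusion.** The point holds as a failure of pre-specification. Section 7 defers the method explicitly and makes it depend on an undefined check, so the primary tests in Studies 2 and 3 can be selected after the results are known. The illustrative cost is a type I error of about 8% instead of 5% in Study 2. This rests on an assumed lognormal shape, an assumed correlation of 0.5, a two-visit comparison rather than all five doses, and outright selection among three tests. It shows what the wording permits and does not predict what the team would do.

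For Study 3 there is also a definite inconsistency: sizing on log AIRg is not matched in the analysis section, and the printed SD of 48.7 is incompatible with 0.79 SD. The former is certain from the text and the latter from arithmetic.

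For Study 2, right skew is likely, but which scale is more powerful is unknown. No fixed power loss follows, and a log-transformed index should not be mandated, since an increase in insulin can be zero or negative.

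**What to change.** In Section 7:

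1. Delete the sentence deferring the method and the condition on normality.
2. **Study 3:** name log AIRg as the primary analysis variable, in a within-person crossover model with period, reported as a propionate-to-placebo ratio with 95% CI. Fix this before unblinding. In Section 3, reconcile the printed SD of 48.7 with the 0.79 SD.
3. **Study 2:** because it is described as open label, fix before data collection one within-person repeated-measures analysis with period, on a stated scale that is defined for zero and negative index values. Add a within-person rank or permutation test as a sensitivity analysis.

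The change is to wording only; no visits, samples or participants are added. The price is that Study 3 effects are reported as ratios, and that the team gives up the freedom to choose the method after seeing the data.
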